4.2.2. Recruitment of Target Population

Subjects with chronic low back pain will be recruited by the investigators, following all HIPAA guidelines, to ascertain their level of interest and willingness to take part in this study. Recruitment materials will be provided to aid in subject enrollment. All recruitment materials will be IRB approved prior to their use. A third-party clinical trial recruitment firm may also be used to support recruitment efforts, such as a toll-free patient information center.

4.2.3.

424

4.2.5. Vulnerable Population

Vulnerable populations, such as prisoners, individuals that report to investigators, or children, are excluded from participation in this study (Section 4.2.1) and will not be enrolled.

4.2.6. Sample Size & Justification

Up to 30 sites will participate in the study. The study will be planned with a maximum sample size of 230 enrolled subjects

Subjects will be randomized to either Group #1 or Group #2 using a 1:1 randomization scheme.

All subjects who sign a consent will receive a subject ID number. Subjects who sign a consent and do not meet all study eligibility criteria will be considered screen failures and not count against the number of enrolled subjects. Subjects who are randomized at Visit 2 will be counted as enrolled. If a subject does not receive the randomized intervention (e.g., complete PNS or receive a standard interventional procedure), their results may be excluded and/or analyzed separately from the rest of the population.

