4.3.1. Primary Endpoints

4.3.1.1. Primary Efficacy Endpoint

The primary outcome of this study will be calculated as the mean score of average daily back pain intensity 3 months after start of treatment to baseline. This will be recorded using Question 5 of the Brief Pain Inventory Short Form (BPI-5; details of BPI below), which assesses “average pain” on an 11-point numerical rating scale, with one end

representing “no pain” (0) and the other end representing “pain as bad as you can imagine” (10). Subjects will record BPI-5 scores daily in a diary, and the mean score for each week will be calculated for each subject. The primary endpoint will be a highly clinically significant reduction in back pain evidenced by $\geq 50\%$ reduction in mean “average pain” (BPI-5) over the week prior to the 3-month follow-up visit (Visit 13) compared to baseline.

The primary endpoint compares the proportion of subjects in Group 1 (PNS) relative to that in Group 2 (standard interventional management) that achieve $\geq 50\%$ reduction in average back pain intensity from baseline to 3-months after start of treatment. This endpoint will examine the statistical non-inferiority of the proportion of clinical successes in Group 1 compared to Group 2, and if non-inferiority is achieved, examine the statistical superiority of the proportion of successes in Group 1 compared to Group 2.

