4.3.2. Secondary Endpoints

Several secondary endpoints will be collected to evaluate what effect, if any, the interventions have on each measure.

Analyses may also explore the effect of the actual intervention(s) received on these secondary endpoints. Secondary efficacy endpoints for the following outcome measures will be assessed at 3 months after start of treatment, unless otherwise stated:

- Proportion success evidenced by $\geq 30\%$ reduction in pain interference as measured using Question #9 of the BPI-SF (BPI-9) compared to baseline
- Proportion with clinically significant change (≥ 10 -point reduction) in disability as measured using the Oswestry Disability Index (ODI) compared to baseline
- Durability of primary endpoint, proportion success with $\geq 50\%$ reduction in average back pain intensity, at 6- to 24-months after start of treatment
- Proportion success with $\geq 50\%$ reduction in worst back pain intensity as measured using Question #3 of the BPI-SF (BPI-3) compared to baseline
- Average Patient Global Impression of Change (PGIC)

- Average change in health-related quality of life as measured using the EQ-5D compared to baseline
- Average change in analgesic medication usage (e.g., opioids, non-opioids, and total analgesic medication usage)

Brief Pain Inventory-Short Form (BPI)

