5.11. Early Study Termination

It is possible that this study may be terminated prior to completing enrollment. As a result of the study design, the results will be reviewed and evaluated throughout the study as each subject completes his/her participation. If the results are less favorable than anticipated the study may be terminated early. Similarly, if it is found that the study yields results that are more favorable than expected, the study may be terminated earlier than expected. Any decision to terminate the study will be promptly reported to the IRBs and HRPO.

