5.12. Subject Crossover

Subjects randomized to the control group (Group 2) may crossover to receive PNS after 12 months (Visit 16). The ability to crossover may depend on Investigator judgement related to the interventional procedure the subject received (e.g., if it conflicts with the SPRINT Instructions for Use).

Group 2 subjects who crossover to receive PNS and complete Visit C1 (lead placement) will then complete study visits to collect outcomes at 1-mo (Visit C2), 2-mo (C3), 3-mo (C4), 6-mo (C5), 9-mo (C6), and 12-mo (C7) after PNS lead placement. Visits C5 through C7 will be completed as phone calls. Outcomes at all crossover visits will be assessed in accordance with Appendix B. Women of childbearing age and reproductive potential will have a pregnancy test completed before or at Visit C1.

[REDACTED]

[REDACTED]

Subjects who are randomized to Group 1 (PNS), but wish to also receive RFA or another standard interventional management may elect to undergo any other treatments for low back pain at any point, however, the use of other therapies or interventions will be collected at study visits. Subjects electing to receive other treatments will still continue participation as Group 1 subjects (i.e., are not discharged from study, continue participation in study visit schedule as normal, and are not crossed over to Group 2 for the purposes of the study).

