7.4. Subject Screening and Identification Log

A subject screening log will be completed at the clinical site for all subjects who were considered for the study. Those individuals who are excluded will be listed along with the reason for exclusion. Any subject who signs an Informed Consent and does not proceed with procedures associated with treatment or fails to meet eligibility (e.g., baseline diary back pain score < 4) will be considered a screen failure. The Subject Identification log will be completed for subjects enrolled in the study.

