7.5. Subject Numbering

Screened and consented consecutive subjects will be given a unique Subject ID number. Subjects who sign consent and do not meet all study eligibility criteria will be considered screen failures and not count against the number of enrolled subjects. Subjects who are randomized at Visit 2 will be counted as enrolled. A number will be assigned consecutively to each subject at each clinical site. A master list linking the subjects to the unique "Subject ID" numbers will be kept by the study staff in a secure location.

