8.0 DATA ANALYSIS AND STATISTICAL METHODS

All primary and secondary outcome data will be analyzed and reported. Each clinical site or individual clinician may be analyzed separately. The study objective is to compare the safety and effectiveness of percutaneous PNS for the treatment of low back pain to standard interventional management. The study will determine if the treatment effect of percutaneous PNS is equivalent (i.e., statistically non-inferior), and if so, if it is superior, to standard treatment with standard interventional management.

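### Section 4.2.6 lets the results of randomized subjects be excluded for events after randomization, and no visible text keeps this out of the primary comparison

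*Protocol*

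**What the plan says.** Section 4.2.6 plans for at most 230 enrolled subjects, randomized 1:1, and treats randomization at Visit 2 as enrolment. Section 7.5 repeats this: "Subjects who are randomized at Visit 2 will be counted as enrolled". Section 4.2.6 then takes up subjects who do not receive the randomized intervention. Its examples are completing PNS and receiving a standard interventional procedure. Of such subjects it says that "their results may be excluded and/or analyzed separately from the rest of the population".

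Other text bears on who is analysed:

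- Section 4.3.1.1 defines the primary comparison by group, first for non-inferiority and then for superiority, without naming an analysis set: "The primary endpoint compares the proportion of subjects in Group 1 (PNS) relative to that in Group 2".
- Section 8.0 says "All primary and secondary outcome data will be analyzed and reported".
- Section 5.12 says "Subjects electing to receive other treatments will still continue participation as Group 1 subjects".
- Section 4.3.2 allows as-received analyses, but ties them to secondary endpoints: "Analyses may also explore the effect of the actual intervention(s) received on these secondary endpoints".
- Section 7.4 extends the label screen failure to "Any subject who signs an Informed Consent and does not proceed with procedures associated with treatment", with no limit to the period before randomization.

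**The concern.** Whether a subject completes PNS or goes on to a procedure is known only after randomization and may be related to outcome. If such subjects are removed from the primary analysis, the groups compared are no longer the ones that randomization made comparable.

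The triggers are not the same in the two arms. Under section 5.3, Group 1 goes on to PNS after a single medial branch block whatever its result, so the likely trigger in that arm is failure to complete stimulation. Section 8.1 names early lead dislodgement or removal as a known cause of data loss. In Group 2, a subject can miss ablation because the diagnostic block failed (section 5.3) or can choose to have no procedure (section 5.4). Exclusion could therefore set PNS completers against diagnostically selected controls.

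The permission is also optional, so the same data could give different primary results depending on whether it is used. Section 5.11 says that "the results will be reviewed and evaluated throughout the study as each subject completes his/her participation". It does not say whether that review is by group, but no visible text keeps a decision to exclude apart from known results.

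**Working it through.** **Step 1: does any visible text confine the permission?**

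| Section | What it does | Does it limit 4.2.6? |
|---|---|---|
| 4.3.1.1 | Compares success proportions by group | No; no analysis set named |
| 8.0 | All outcome data analysed and reported | No; this is compatible with separate analysis |
| 5.12 | Group 1 subjects who take other treatments stay in Group 1 | No; it does not address non-completion |
| 4.3.2 | As-received analyses for secondary endpoints | No; it adds a permission elsewhere |
| 5.3, 5.4, 8.1 | Untreated subjects can stay in follow-up | No; this concerns data collection, not analysis |

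Nothing cancels the sentence. Section 4.3.2 shows that such a permission can be tied to named endpoints; section 4.2.6 has no such tie.

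**Step 2: inputs for size.** From the protocol: 230 subjects at 1:1, so 230/2 = 115 per arm. The success rates, exclusion fractions, prognosis gaps and margin below are all assumptions. The sample size itself cannot be reproduced, because none of its inputs is visible.

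**Step 3: shift in an arm's success rate.** Let p be the rate in the whole arm, q the fraction dropped, and gap the kept rate minus the dropped rate. Since p = (1 − q) × kept + q × dropped, it follows that kept = p + q × gap.

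- q = 0.15: shift 0.15 × (0.10 to 0.40) = 1.5 to 6 points.
- q = 0.30: shift 0.30 × (0.10 to 0.40) = 3 to 12 points.

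For scale, the 95% confidence half-width for the difference at 40% in both arms is 1.96 × √(2 × 0.4 × 0.6 / 115) = 12.7 points. The shift is smaller than the random error, so its effect shows mainly in the error rate.

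**Step 4: false superiority.** Exact binomial enumeration, true rate 40% in both arms, pooled z > 1.96. Group sizes after dropping are 98 (15% dropped) and 80 (30% dropped).

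| Dropped | Gap in points (kept minus dropped) | Probability |
|---|---|---|
| None | – | 2.6% |
| 15% of Group 1 | 10 / 20 / 30 / 40 | 4.2 / 6.5 / 9.8 / 14.2% |
| 30% of Group 2 | 10 / 20 / 30 / 40 | 0.89 / 0.27 / 0.07 / 0.02% |
| 30% of Group 2 | −10 / −20 | 6.3 / 13.5% |
| 15% of each arm, equal gaps | 10 to 40 | 2.5 to 2.6% |
| 15% of Group 1 and 30% of Group 2 | 20 and 10 | 2.5% |
| 15% of Group 1 and 30% of Group 2 | 10 to 40 in each | 0.04 to 6.0% |
| 15% of Group 1 and 30% of Group 2 | 10 to 40 and −10 to −20 | 8.7 to 36.7% |

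In the row with gaps of 10 to 40 in each arm, 14 of the 16 pairs stay at or below the 2.6% baseline. The other two are 3.9% (gaps 30 and 10) and 6.0% (gaps 40 and 10).

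**Step 5: false non-inferiority.** Unpooled z of (difference + margin) > 1.96, with the true difference set at the margin.

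- Assumed margin 10 points (30% v 40%): 2.6% with all randomized. Dropping 15% of Group 1 gives 4.1 / 6.6 / 10.1% for gaps of 10 / 20 / 30. A gap of 40 is impossible, because the dropped rate would be negative. Dropping 30% of Group 2 gives 0.9% down to 0.01% for gaps of 10 to 40, and 6.9 to 15.0% for gaps of −10 to −20. Dropping from both arms at gaps of 20 and 10 gives 2.6%.
- Assumed margin 15 points (25% v 40%): 2.5% with all randomized. Dropping 15% of Group 1 gives 4.2 / 6.8% for gaps of 10 / 20. Dropping from both arms at gaps of 20 and 10 gives 2.5%.

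**Step 6: the related label.** Sections 4.2.6 and 7.5 treat randomized subjects as enrolled, yet also call any consented subject who fails an eligibility criterion a screen failure. Pregnancy is an exclusion checked after randomization, in Group 1 only (sections 4.2.1 and 5.4), so this label can fall on a randomized subject in one arm only. Section 7.4 extends it to anyone who does not proceed to treatment procedures, although sections 5.3, 5.4 and 8.1 provide for untreated Group 2 subjects to stay in study visits.

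**The case against.** Analysis sets usually belong in the SAP, which is not at hand, and the sentence says only that results may be excluded. It can be read as a placeholder for per-protocol or as-treated sets. Parts of 4.2.6 are missing from the public copy, and section 4.2.4 on subject disposition is listed in the contents but unreadable; either could settle the matter. The rest of the protocol leans toward analysis as assigned. The error rates rest on assumed inputs, and where poor responders are dropped from both arms most cases show no inflation. Section 5.11 concerns early termination, not analysis sets. The screen-failure wording is a labelling matter. In the non-inferiority step, an all-randomized analysis can itself pull the groups together.

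Much of this stands as a limit. It cannot be said that the trial will exclude these subjects from the primary analysis, and the size is not known. Section 5.11 is supporting context only, and the labelling point is minor. The core point survives. The protocol states a permission; it does not merely leave out a detail. If the SAP fixes an all-randomized primary set, section 4.2.6 still contradicts it and needs the same correction. The non-inferiority objection is a reason to report a pre-defined restricted analysis beside the primary one. It is no reason to keep an open option.

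**Conclusion.** The concern holds. As written, section 4.2.6 permits a discretionary exclusion of enrolled subjects after randomization, with triggers that differ by arm, and nothing visible keeps it from the primary non-inferiority and superiority tests. The bias can run either way. It comes from imbalance between the arms in how many are dropped and how they fared: balanced dropping does no harm to the error rate, while one-sided dropping under the assumptions above moves a nominal 2.5% test anywhere from 0.01% to about 15%. These figures show what is possible; they do not estimate what will happen in this trial. The wording must be corrected before by-group results are seen. Confidence is high that the permission exists and is unconfined in the visible text. Whether it would be used cannot be told from the protocol.

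**What to change.** Replace the sentence in section 4.2.6 with wording to this effect:

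> The primary analysis includes every randomized subject in the assigned group, whatever was received or completed. Any analysis restricted to subjects who received or completed the intervention is supportive, is defined before by-group results are seen, and is reported beside the primary one, including for non-inferiority.

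In sections 4.2.6, 7.4 and 7.5, limit the term screen failure to subjects who were not randomized. A Group 1 subject found pregnant after randomization then stays counted as enrolled; this concerns labelling and analysis only, not treatment.

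The cost is wording in three sections. Many of these subjects may remain in follow-up, but sections 5.4, 5.9 and 8.1 make continuation optional, so some 3-month outcomes may be missing and will fall under the plan's missing-data rules. The PNS success rate may be slightly lower once non-completers are included.

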4.2.7. Concurrent Medications and Non-Drug Therapies

All interventions targeting pain control will be recorded in the Case Report Forms (CRF) and subject diaries.

Subjects will be permitted to use analgesic medications (opioid or non-opioid) as prescribed/recommended by their physician and analgesic usage will be recorded. However, to qualify for enrollment, their current medication or therapy history must have been stable for at least 4 weeks. Subjects will be asked to indicate the reason for use (e.g., back pain, or other pain such as headache, leg pain, toothache, etc.). Subjects using other therapies will continue to participate in the study visits, but will be asked to report the use of other therapies or changes in medications at study visits.

4.3. Study Endpoints

Outcomes and exploratory measures will be collected per Appendix B.

4.3.1. Primary Endpoints

4.3.1.1. Primary Efficacy Endpoint

The primary outcome of this study will be calculated as the mean score of average daily back pain intensity 3 months after start of treatment to baseline. This will be recorded using Question 5 of the Brief Pain Inventory Short Form (BPI-5; details of BPI below), which assesses “average pain” on an 11-point numerical rating scale, with one end

representing “no pain” (0) and the other end representing “pain as bad as you can imagine” (10). Subjects will record BPI-5 scores daily in a diary, and the mean score for each week will be calculated for each subject. The primary endpoint will be a highly clinically significant reduction in back pain evidenced by $\geq 50\%$ reduction in mean “average pain” (BPI-5) over the week prior to the 3-month follow-up visit (Visit 13) compared to baseline.

The primary endpoint compares the proportion of subjects in Group 1 (PNS) relative to that in Group 2 (standard interventional management) that achieve $\geq 50\%$ reduction in average back pain intensity from baseline to 3-months after start of treatment. This endpoint will examine the statistical non-inferiority of the proportion of clinical successes in Group 1 compared to Group 2, and if non-inferiority is achieved, examine the statistical superiority of the proportion of successes in Group 1 compared to Group 2.

4.3.1.2. Primary Safety Endpoint

The primary safety endpoint is the occurrence and type of study-related adverse events. For Group 1 (PNS), all adverse device effects (ADEs) that occur during the study will be documented. For group 2 (standard interventional management), all study-related adverse events will be documented. For both groups, AEs related to standard of care (SOC) will be collected. Specific details regarding any study-related AE will be collected on an Adverse Event Form and will be followed to resolution. The investigator will determine the severity of each event as well as its relationship to the study (i.e., device and procedure). In addition, each event will be categorized as either serious or non-serious. Any necessary treatment or intervention required and the resolution status of the event will also be documented. Study-related AEs will be tabulated and summarized at the conclusion of study. Additional details on the monitoring and adjudication of study-related AEs is described in the section regarding monitoring.

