5.3. Visit 3 – Medial Branch Block or Diagnostic Procedures

A diagnostic medial branch block (MBB) or other diagnostic procedure (e.g., SCS trial, imaging, etc.), as deemed appropriate by the physician for subjects in Group 2, will be completed at or following Visit 3. Visits 2 and 3 may occur on the same day.

The following measures will be assessed at this visit for both groups:

- Selected questions from Brief Pain Inventory (BPI) (e.g., BPI-3, BPI-5)
- Current pain treatments/analgesic usage

GROUP 1 – Medial Branch Block

Subjects will undergo a standard diagnostic medial branch block (MBB) targeting the area where they have chronic low back pain. Provocative maneuvers or positions which normally exacerbate their typical pain may also be assessed and documented before and after the procedure to help determine effect of MBB.

The diagnostic medial branch block (MBB) will be performed according to standard practice using aseptic technique. [REDACTED]

[REDACTED]

[REDACTED]

[REDACTED]

[REDACTED]

Pain scores will be collected post-procedure to evaluate the impact of the MBB. Subjects in Group 1 (PNS) will proceed to Visit 4 (PNS Lead Placement) after a single MBB (Visit 3), regardless of the outcome.

If a subject has previously undergone a diagnostic lumbar medial branch block (MBB) within 3 months of the baseline visit, and results and medical records are available from that block, a subject is not required to complete an additional block at this visit. However, procedure details and results from the procedure should be documented in the CRFs. If a subject previously underwent the MBB and results are not available, the subject should complete the visit, repeating the MBB as part of the study.

GROUP 2 - Diagnostic Procedures

Subjects in Group 2 will receive standard of care diagnostic testing and/or interventions (e.g., Medial Branch Block, SCS trial, MRI, etc.) for their low back pain as they usually would if not participating in the study. All diagnostic tests or interventions received by Group 2 subjects will not be paid for through the study. Subjects should follow their insurance requirements (e.g., prior authorization) for these procedures. [REDACTED]

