10.2. Known and Anticipated Risks

The known and anticipated risks summarized below are described as expected to be either common (occurring about 10% of the time), uncommon (occurring about 1-10% of the time), or rare (occurring less than 1% of the time). Group #2 subjects will be receiving

therapies that they would normally receive if they were not participating in the study, only the risks that are specific to the study are detailed below.

[figure not shown]
[figure not shown]
The following risks apply to the subjects who receive PNS:

Risks associated with insertion of the needle introducer for lead placement

[figure not shown]
Risk of skin irritation, infection, or inflammation at the lead exit sites

Risk of the percutaneous lead breaking beneath the skin

Risk of skin irritation under the pad or bandages

Risk of discomfort or increased pain

SPR Therapeutics, Inc.
0151-CSP-000

CONFIDENTIAL
Page 48 of 62

[REDACTED]

[figure not shown]
[REDACTED]

[REDACTED]

[REDACTED]

[REDACTED]

[REDACTED]

Risks associated with medial branch block

Risk of loss of confidentiality

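### Sections 4.3.1.2, 8.2 and 9.6 disagree on whether standard-of-care events count as study-related, so the primary safety endpoint can be counted differently in the two groups

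*Protocol*

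**What the plan says.** **Section 4.3.1.2** defines the endpoint: "The primary safety endpoint is the occurrence and type of study-related adverse events". It then uses three labels.
- Group 1: "For Group 1 (PNS), all adverse device effects (ADEs) that occur during the study will be documented".
- Group 2: the events to be documented are the study-related ones.
- Both groups: "For both groups, AEs related to standard of care (SOC) will be collected".

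The investigator judges each event's "relationship to the study (i.e., device and procedure"), and the section ends its counting rule with "Study-related AEs will be tabulated and summarized at the conclusion of study".

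**Section 8.2**, the safety analysis section, names study-related events and does not mention SOC events.

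**Section 9.6** says that an adverse device effect (ADE) is a study-related adverse event and that ADEs take in events related to SOC. It also says that adverse events are not captured unless they are study-related or their relationship cannot be determined.

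**Section 5.3** makes a medial branch block (MBB) part of the Group 1 pathway, waived if a documented block was done within 3 months of baseline. For Group 2 it says "Subjects in Group 2 will receive standard of care diagnostic testing and/or interventions", and gives the MBB as one example. Section 10.2 reasons in the same way: Group 2 has therapies that it would have had anyway, so "only the risks that are specific to the study are detailed below".

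**Section 8.0** states the objective, which is to "compare the safety and effectiveness of percutaneous PNS for the treatment of low back pain to standard interventional management".

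**The concern.** A safety comparison needs the same kind of event to be counted by the same rule in both groups. Here the rule turns on the term study-related, and the protocol uses that term in two ways. Take a pain flare after an MBB. In Group 1 the block is done because the protocol calls for it, so the flare is readily classed as related to a study procedure. In Group 2 the block carries the SOC label, so the same flare can be placed in the class that is collected but not named for tabulation. The same can happen to each group's main treatment: lead placement and the device on one side, radiofrequency ablation (RFA), spinal cord stimulation (SCS) or surgery on the other.

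Attribution is made by investigators during the trial. Under Section 9.4 it is settled by a clinical events reviewer who is told the group assignment. If they apply different rules, a table built later inherits the difference. What is at stake is whether the primary safety endpoint can serve the comparison that Section 8.0 promises.

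**Working it through.** The protocol gives no safety figure to reproduce, so the check is first a comparison of texts and then an illustration of size.

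**1. The texts side by side**

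| Question | Section 4.3.1.2 (with 8.2) | Section 9.6 |
|---|---|---|
| Is an SOC event study-related? | Not stated; SOC has a separate sentence | Yes: ADEs include SOC events, and ADEs are study-related events |
| Is it recorded? | Yes, in both groups | Yes if study-related; otherwise barred, unless the relationship is undeterminable |
| Is it tabulated in the endpoint? | Not stated; only study-related events are named | Yes, by implication |

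There are two ways to read these together.
- *SOC events are study-related.* Sections 4.3.1.2 and 9.6 then agree that they are recorded, and they enter the table. The separate SOC sentence in 4.3.1.2 becomes redundant, and a complication of RFA or surgery is called a device effect, although 9.6 also speaks of relationship to the System.
- *SOC events are not study-related.* The separate sentence in 4.3.1.2 then has a purpose, but the capture rule in 9.6 bars events that 4.3.1.2 says are collected.

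Neither reading leaves every sentence intact. A site working from 4.3.1.2 and a site working from 9.6 could count differently.

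**2. Illustration of size**

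Inputs:
- n = 115 per group, from the maximum of 230 randomized 1:1 (Section 4.2.6): 230 / 2 = 115.
- r = true risk of a procedure- or treatment-related event, assumed equal in both groups. Values of 1%, 5% and 10% are assumptions. They span the band that Section 10.2 calls uncommon, but the visible text assigns no such band to the MBB or to Group 2 procedures.
- f = share of Group 2 events that are counted: 0 (all left out), 0.5, or 1 (Section 9.6 reading).

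Formulas: expected counts are n × r in Group 1 and n × r × f in Group 2; the spurious difference is r × (1 − f). The last column is the exact probability of a two-sided Fisher p<0.05 with independent binomial counts.

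| r | f | Expected counts | Spurious difference | P(Fisher p<0.05) |
|---|---|---|---|---|
| 1% | 0 | 1.15 v 0 | 1 point | 0.001 |
| 1% | 0.5 | 1.15 v 0.58 | 0.5 points | 0.001 |
| 1% | 1 | 1.15 v 1.15 | 0 | 0.001 |
| 5% | 0 | 5.75 v 0 | 5 points | 0.52 |
| 5% | 0.5 | 5.75 v 2.88 | 2.5 points | 0.08 |
| 5% | 1 | 5.75 v 5.75 | 0 | 0.02 |
| 10% | 0 | 11.5 v 0 | 10 points | 0.98 |
| 10% | 0.5 | 11.5 v 5.75 | 5 points | 0.21 |
| 10% | 1 | 11.5 v 11.5 | 0 | 0.03 |

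The f = 0 rows can be checked by hand. With no events in Group 2, five in Group 1 give p = 0.060 and six give p = 0.029, so the test crosses 0.05 at six. P(X ≥ 6) for a binomial with n = 115 is 0.52 at 5% and 0.98 at 10%.

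**The case against.** The strongest reply is that Section 9.6 is the only place that explains what study-related covers, and it puts SOC events inside. It also reconciles best with the instruction to collect SOC events in both groups. On that reading nothing is left out. Several details support it:
- The tabulation sentence contains no exclusion.
- The requirement to document study-related events in Group 2 would have little content if Group 2's own procedures could not produce any.
- The relationship judgement refers to device and procedure, without limiting the procedure to Group 1.
- The SOC sentence applies to both groups, and Section 5.3 itself describes the Group 1 block as a standard one.
- Adverse events after Group 2 diagnostic procedures are recorded, and all adverse events go to adjudication.
- Section 10.2 concerns risk disclosure and does not define the endpoint.
- Table layout is ordinarily left to the SAP, which is not at hand.

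Much of this stands. A reader might infer from 4.3.1.2 alone that Group 2's procedure harms are excluded and that the safety comparison is therefore biased. The protocol does not support that: no section states the exclusion, and 9.6 points the other way. Nor can the 52% and 98% figures be read as the trial's error rate. They need every Group 2 event to be left out, assumed event rates, and a test that the protocol does not specify.

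What does not stand is that the matter is only one of layout. The sections conflict on what a primary endpoint counts, and the attribution is made at the sites and by the adjudicator before any table is designed. A SAP table cannot restore a uniform rule if events were attributed under two.

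**Conclusion.** The concern holds as an inconsistency that permits asymmetric counting; it does not establish a bias. Sections 4.3.1.2, 8.2 and 9.6 do not agree on whether SOC events belong to the primary safety endpoint. Because the SOC label attaches to Group 2's diagnostic work and interventions while Group 1's block and lead placement are protocol procedures, any loss of events under the 4.3.1.2 wording would fall mainly on Group 2 and make PNS look worse than it is. Under the 9.6 wording the tilt is zero.

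The size therefore depends on which wording is followed. At an assumed common risk of 5% to 10%, the spurious difference runs from 0 points (all Group 2 events counted), through 2.5 to 5 points (half counted), to 5 to 10 points (none counted). At an assumed 1% it is at most 1 point, and a spurious significant result is very unlikely. These figures rest on 115 per group, equal true risks and event rates that the protocol does not give. The text should be corrected, because comparing safety is a stated objective and the correction is cheap.

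**What to change.** Use one arm-neutral definition in Sections 4.3.1.2, 8.2 and 9.6, for example:

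*The primary safety endpoint is the occurrence and type of adverse events related to the diagnostic procedure(s) or treatment received under the assigned strategy, in either group. In Group 1 this covers the MBB, lead placement, the device and lead removal. In Group 2 it covers the diagnostic procedures and the standard interventional management received.*

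Then:
- replace the separate Group 1 and Group 2 labels in 4.3.1.2 with this definition, and say that these events are tabulated by group, side by side;
- align the capture rule and the ADE definition in 9.6, so that SOC-related events are clearly captured and are not called device effects;
- keep SPRINT-device-related events as a sub-table for device reporting;
- give investigators and the clinical events reviewer the same definition, and apply it to events already attributed.

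The cost is wording in three sections, one re-specified table and a check of existing attributions. SOC-related events are already to be collected in both groups, so no new data collection is needed.
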